50–100 selected patients presenting to the Emergency Department of UZ Brussel. Patients will be selected according to the predefined inclusion and exclusion criteria. Study period: September 2020 – February 2022 (maximum). Based on estimates from 2018 data at UZ Brussel (approximately 1800 sutures per year), the required data could likely be collected within 1–2 months.

Procedure

All selected patients will be treated by the attending physician for their open wound. Based on the physician's treatment plan, the patient will be assigned to either the LAT gel group or the lidocaine group. Pain during administration of the anesthetic will be recorded by the treating physician using a Visual Analogue Scale (VAS). Immediately after patient contact, the physician will complete additional information regarding patient and wound characteristics on a data collection form prepared by the researchers. In the lidocaine group, lidocaine infiltration will be administered immediately before suturing. A VAS score will also be obtained and documented on the designated form. After 30 minutes (LAT gel group) or 5 minutes (lidocaine infiltration group), the effectiveness of the anesthesia will be assessed using a 25G needle prick, and documented by the treating physician using the VAS. If the anesthesia is insufficient, additional lidocaine infiltration will be administered and documented on the same form. If sufficient anesthesia is achieved, the treating physician will suture the wound according to the UZ Brussel hospital protocol. During suturing, pain experience will again be assessed using a VAS and recorded on the form together with the physician's observations regarding the characteristics of the suturing procedure. Further data analysis will be performed by the investigators.

*Analysis**Primary analysis*

The first analysis will determine whether LAT gel reduces pain experience compared with lidocaine infiltration, specifically during:

- Administration of the anesthetic
- Testing of the anesthesia
- Suturing

Sub-analyses:

The following aspects will also be analyzed:

- Wound Characteristics
 - o Length and location (skull, face, fingers, toes, lower limb, upper limb, trunk)
- Suturing Characteristics
 - o Number of sutures
 - o Duration of suturing
 - o Suturing technique (sutures, staples, glue, other)
- Patient Characteristics
 - o Age
 - o Seks
 - o Weight
- Medication
 - o Dose of LAT gel
 - o Dose of lidocaine
 - o (+ additional doses if required)

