Statistical Analysis Plan:

Data entry will be performed in Excel.

Further statistical processing will be performed in SPSS using ANCOVA.

Publication Policy / Agreements:

- **Thesis:** [name], supervisor [name], co-supervisor [name]
- **Poster and presentation:** [name], supervisor/[name], co-supervisor [name]
- **Scientific article:** [name] – [name]– [name]

Referenties

Short Study Protocol

Title

Lidocaine–adrenaline–tetracaine gel (LAT gel) vs lidocaine infiltration as local anesthesia for suturing a superficial wound: a comparative study in adults.

Brief Description of the Proposed Content

Problem Statement

UZ Brussel has a busy emergency department where patients are triaged into urgent care, trauma care, and pediatric care. Trauma care frequently treats patients with wounds requiring suturing. At UZ Brussel, the standard local anesthesia for suturing wounds in adults is infiltration anesthesia with lidocaine. However, other (topical) treatments exist. In children at UZ Brussel, LAT gel is already used. Adult patients frequently complain about the additional pain caused by lidocaine injection. Moreover, the injection has been described as making the technical act of suturing more difficult. The increased risk of needle–stick injuries is another disadvantage. In children, LAT gel has been implemented precisely because of this pain complaint. Studies also show that injection pain increases the risk of needle phobia. Furthermore, applying LAT gel in an anxious or restless child is technically easier than administering a lidocaine injection.

Short Description:

The study could therefore provide an indication of which form of local anesthesia in adults is preferable with regard to pain experience during administration of the anesthetic and during suturing.

Method

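### Treatment is chosen by the physician, but no pain score before the anaesthetic is described and the ANCOVA names no covariates, so presenting pain cannot be adjusted for

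*Combined protocol and SAP*

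**What the plan says.** The Statistical Analysis Plan section of the Extended Study Protocol names Excel for data entry and then says: "Further statistical processing will be performed in SPSS using ANCOVA". It gives no model, no covariates and no rule for handling the three pain outcomes.

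The Procedure section, repeated in substance under Method in the Short Study Protocol, describes three scores:

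- Administration: "Pain during administration of the anesthetic will be recorded by the treating physician using a Visual Analogue Scale (VAS").
- Test, at 30 minutes (LAT gel) or 5 minutes (lidocaine): "the effectiveness of the anesthesia will be assessed using a 25G needle prick, and documented by the treating physician using the VAS".
- Suturing: "During suturing, pain experience will again be assessed using a VAS".

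No score before the anaesthetic is described. The same section lets the physician's treatment plan decide the group. On timing it says: "Immediately after patient contact, the physician will complete additional information regarding patient and wound characteristics".

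The only list of further variables is under Sub-analyses, introduced by "The following aspects will also be analyzed". It contains pre-treatment factors (wound length and location, age, sex, weight). It also contains items that follow or define treatment: "Number of sutures", "Duration of suturing", technique, the LAT gel and lidocaine doses, and additional doses. No sentence links this list to the ANCOVA.

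**The concern.** Without randomisation, covariate adjustment is the only analytic control of confounding that the plan offers, and its content is blank. If physicians choose between gel and infiltration partly by how much pain the patient already has, or by wound features that go with pain, the groups differ before treatment starts. The first recorded score is already an outcome, so it cannot serve as the baseline. In both groups it combines existing wound pain with pain from giving the anaesthetic.

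A second risk follows from the open model. An analyst looking for covariates will find only the Sub-analyses list, and some of its items should not be adjusted for when the question is the effect of the anaesthetic.

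**Working it through.** **The plan's own figure.** The Short Study Protocol asks for at least 70 patients from a power calculation; the Extended Study Protocol says 50–100. No inputs are given, so 70 cannot be reproduced. Assuming 1:1 groups, two-sided 0.05 and 80% power (normal approximation), the detectable difference is (1.960 + 0.842) × √(2/35) = 0.67 SD. It would be 0.79 SD at N = 50 and 0.56 SD at N = 100.

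**Inputs not in the documents.** Let r be the within-group correlation of pre-anaesthetic pain with a later score, and c the correlation of pre-anaesthetic pain with group. I take r = 0.3 and 0.5, and c = 0, 0.2 and 0.3. All are assumptions, and r may differ between the three scores.

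**Confounding.** With 1:1 groups, correlation c corresponds to a baseline difference D = 2c/√(1 − c²) in within-group SDs:

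- c = 0.2: 0.4/0.980 = 0.41
- c = 0.3: 0.6/0.954 = 0.63

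The unadjusted comparison is then shifted by r × D, in outcome SDs.

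**Precision.** Adjustment multiplies the variance of the group effect by (1 − r²)/(1 − c²), so the equivalent unadjusted sample size is 70 × (1 − c²)/(1 − r²).

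| r | c | Shift r × D (SD) | Equivalent N |
|---|---|---|---|
| 0.3 | 0 | 0 | 77 |
| 0.3 | 0.2 | 0.12 | 74 |
| 0.3 | 0.3 | 0.19 | 70 |
| 0.5 | 0 | 0 | 93 |
| 0.5 | 0.2 | 0.20 | 90 |
| 0.5 | 0.3 | 0.31 | 85 |

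Where baseline pain is unbalanced, the shift runs from 0.12/0.67 = 18% to 0.31/0.67 = 46% of the detectable difference, in a direction the documents do not indicate. At c = 0 the detectable difference falls to 0.67 × √0.91 = 0.64 SD (r = 0.3) or 0.67 × √0.75 = 0.58 SD (r = 0.5). These are upper bounds on the gain: imbalance reduces it, and wound length, location, age and sex would already explain part of the same variance.

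**Variables to keep out.**

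- *LAT gel dose.* The Materials list gives 2 mL per patient in the LAT gel group. With intercept, group and a dose of 2 mL or 0, the design matrix has rank 2 of 3, so the group effect cannot be estimated. If some patients received less (shortfall simulated as half-normal with scale 0.3 or 0.5 mL), the variance inflation factor is about 54 or 17.
- *Suturing characteristics and additional lidocaine.* These arise after the administration and test scores, so they can absorb effect only on the suturing score. Take a true effect of −0.67 SD, with assumed paths a (treatment to the variable) and b (the variable to pain). The adjusted estimate is −0.67 + ab: −0.58 at a = b = 0.3 (0.09/0.67 = 13% lost) and −0.31 at a = b = 0.6 (0.36/0.67 = 54% lost).

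**The case against.** The strongest reply is that the plan is thin rather than wrong. Wound length, location, age, sex and weight are collected and precede treatment, so an ANCOVA is feasible without a baseline score. The stated objective is pain experience, so total pain during administration may be what is wanted. The data collection form and flow chart are not shown, so a baseline mark there cannot be excluded.

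Much of this stands. It does not answer the main point: the listed characteristics are not a measure of presenting pain, and the procedure text describes none.

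A reader might also infer more than the documents support:

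- *That the plan adjusts for post-treatment variables.* It does not say so. They are sub-analysis items; the open model permits this error but does not state it.
- *That adjusting away threatens all three scores.* For suturing characteristics and additional lidocaine it can reach only the suturing score.
- *That baseline pain is the best predictor of later pain, or that 70 patients would certainly work like 93.* The documents give no correlation, and 93 is the most favourable case at r = 0.5.
- *That existing wound pain affects the administration score only in the LAT gel group.* It enters in both.
- *That every form entry is made with all pain scores known.* The after-contact timing is stated for patient and wound characteristics. Age and sex could hardly be distorted by it; a wound length recorded late might be.

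**Conclusion.** The point holds as a cheap improvement. As described, the trial compares physician-chosen groups without a measure of pain before the anaesthetic and without a named covariate, so a difference in presenting pain cannot be removed from any of the three comparisons. Its actual size is unknown. Under the assumed correlations with imbalance it is about 0.12 to 0.31 SD, and it is zero if the groups happen to be balanced on presenting pain. Less confounding is the main benefit; better precision is secondary and, at r = 0.3, may be nil. Adjustment would not make the comparison equivalent to a randomised one, because other reasons for the physician's choice may remain unmeasured.

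**What to change.** 1. Add one VAS mark before any anaesthetic is applied, and record wound length and location at that moment.
2. State in the SAP that each of the three scores is analysed by ANCOVA with group, pre-anaesthetic VAS, wound length, location, age and sex. Say in advance whether the seven locations are grouped.
3. State that number of sutures, duration, technique, doses and additional doses are reported by group and do not enter these models.

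The cost is one extra mark per patient, a reordered form, a short SAP addition and some degrees of freedom. With all seven locations kept, the covariates use 1 + 1 + 6 + 1 + 1 = 10, leaving 70 − 12 = 58 residual degrees of freedom instead of 68; grouping locations reduces this cost. If enrolment is already complete, the baseline score cannot be recovered. Items 2 (without the baseline term) and 3 can still be fixed before analysis, and the missing baseline should then be reported as a limitation.

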Extended Study Protocol

Title:

Lidocaine-Adrenaline-Tetracaine gel (LAT gel) vs lidocaine infiltration as local anesthesia for suturing a superficial wound: a comparative study in adults.

Investigators:

- [name]
- Prof dr. [name]
- [name]

Sponsor:

Vrije Universiteit Brussel

Introduction

UZ Brussel has a busy emergency department where patients are triaged upon arrival. Depending on the pathology, they are referred to urgent care (internal medicine pathology), trauma care (orthopedic and surgical emergencies), or pediatric care (pediatric emergencies). Patients presenting with wounds requiring suturing are frequently triaged to the trauma care unit.

At UZ Brussel, the standard local anesthesia for suturing a wound in adults is always an infiltration anesthetic (such as lidocaine). However, other (topical) treatments exist. For example, LAT gel is used in children at UZ Brussel.

Adult patients frequently complain about the additional pain caused by the lidocaine injection. Moreover, it has previously been described that the injection can make the technical procedure of suturing more difficult. Additionally, the increased risk of needle-stick injuries argues against lidocaine injection.

In children, LAT gel has been implemented precisely for these reasons. Studies also show that the additional pain caused by injections increases the risk of developing needle anxiety. Furthermore, the technical procedure of applying LAT gel in a restless and anxious child is much easier than administering a lidocaine injection.

LAT gel consists of lidocaine 4% (80 mg), adrenaline 0.1% (2 mg), tetracaine 0.5% (10 mg), and hypromellose gel. It is a gel that can be prepared magistally and sterily by the pharmacy in a 2 mL syringe with a Luer cap. It should be stored in the refrigerator to maintain optimal consistency and to achieve a shelf life of three months. The gel is not classified as a narcotic, therefore a prescription for narcotic substances is not required.

Ernst et al. (1) already investigated the difference in pain experience between LAT gel and lidocaine injection in 1997. Vandamme et al. (2) wrote a similar article but with a retrospective study design. Adler et al. (3) also compared LAT gel with placebo. All three studies conclude that LAT gel is at least equivalent to lidocaine infiltration. The literature regarding the use of LAT gel in children is much more extensive and justifies its standard use in pediatric patients.

Objective

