The objective of this study is to document and compare the pain experience of a patient requiring suturing between anesthesia with LAT gel and anesthesia with lidocaine infiltration.

This study could therefore provide an indication of which form of local anesthesia in adults is preferable in terms of pain experience, both during administration of the anesthetic and during suturing.

Hypothesis (H1):

LAT gel results in less severe pain during administration, during testing of the anesthesia, and during suturing compared with lidocaine infiltration.

Hypothesis (H2):

LAT gel results in more severe pain during administration, during testing of the anesthesia, and during suturing compared with lidocaine infiltration.

Null hypothesis (H0)

LAT gel results in a similar pain experience during administration, testing of anesthesia, and suturing compared with lidocaine infiltration.

Department Involved in the Study

Emergency Department, UZ Brussel

[name]

[name]

Belgium

Prof. dr. [name]: Supervisor en promotor.

Methods

Study design

Comparative prospective monocentric study.

Materials

- **Electronic Medical Record: Emergency report**
- **2 mL LAT gel (4% lidocaine, 1:1000 epinephrine, 0.5% tetracaine) per patient in the LAT gel group – treatment option**
- **Maximum 4.5 mg/kg 1% lidocaine per patient or maximum 7 mg/kg 1% lidocaine with epinephrine per patient – treatment option**
- **Suturing materials as described in the hospital protocol**
- **Linear Visual Analogue Scale (VAS)**
- **Ruler**
- **Physician data collection form**

Study Population

Inclusion Criteria:

- Adults
- Wounds ≤ 7 cm
- Wounds suitable for single-layer closure
- No mucosal involvement or wounds in the direct vicinity of mucosa

Exclusion Criteria:

- Age < 18 years
- Suspected nerve injury
- Suspected tendon injury
- Wounds located on the genitalia, nose, or ears
- Substance intoxication
- Substance abuse
- Additional sedation with nitrous oxide (NO)
- Pregnancy
- Glaucoma
- Allergy to the described anesthetic agents or preservatives
- Wounds older than 8 hours
- Contaminated wounds
- History of cardiac disease
- History of respiratory disease
- Altered mental status
- Inability to use or interpret the visual analogue scale
- Inability to experience or report pain

Target Population Size:

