All selected patients will be treated by the attending physician for their open wound. Based on the physician's treatment plan, the patient will be assigned to either the LAT gel group or the lidocaine group. Pain during anesthetic administration will be recorded by the physician using a Visual Analogue Scale (VAS). Immediately after patient contact, the physician will complete additional data regarding patient and wound characteristics on a form prepared by the investigators. In the lidocaine group, lidocaine infiltration will be administered just before suturing, and a VAS score will also be recorded. After 30 minutes (LAT gel group) or 5 minutes (lidocaine infiltration group), the effectiveness of anesthesia will be tested using a 25G needle prick and documented using a VAS. If anesthesia is insufficient, additional lidocaine infiltration will be administered and recorded. If anesthesia is adequate, the physician will suture the wound according to the hospital protocol. Pain during suturing will again be assessed using the VAS and recorded together with the physician's observations. Further analysis will be performed by the investigators.

Study population

At least 70 selected patients presenting to the Emergency Department of UZ Brussel. Patients will be selected using the predefined inclusion and exclusion criteria. Study period: September 2020 – February 2022. The number of patients was calculated based on internal data and a power calculation.

Improvement Pathway

If the hypothesis is confirmed, lidocaine infiltration could potentially be replaced by LAT gel application for specific indications (based on the study's inclusion and exclusion criteria).

Lidocaine infiltration could then serve as an alternative or additional local anesthetic, with the aim of reducing patient pain experience.

Intended objective

Hypothesis (H1): LAT gel results in less severe pain during administration, testing of anesthesia, and suturing compared with lidocaine infiltration.

Sub-analysis:

- Wound characteristics
- Suturing characteristics
- Patient characteristics
- Need for additional lidocaine administration

Flow chart

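### The planned ANCOVA assumes one common residual variance, but physician-chosen groups may be unequal in size; if VAS spread also differs, its 5% level and 95% intervals fail, and HC3 standard errors should be specified.

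*Combined protocol and SAP*

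**What the plan says.** The Statistical Analysis Plan in the Extended Study Protocol has two sentences, one on data entry and one on method: "Further statistical processing will be performed in SPSS using ANCOVA". It names no covariates, variance assumption, residual check, robust standard error or alternative method.

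The outcome is a linear VAS. Under Analysis, the primary aim reads "The first analysis will determine whether LAT gel reduces pain experience compared with lidocaine infiltration, specifically during" three moments: administration, testing and suturing.

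The Procedure section, repeated in the Short Study Protocol, forms the groups as follows: "Based on the physician's treatment plan, the patient will be assigned to either the LAT gel group or the lidocaine group". Neither text gives a ratio or a quota per group. The Introduction says that at this hospital "the standard local anesthesia for suturing a wound in adults is always an infiltration anesthetic".

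The total is "50–100 selected patients presenting to the Emergency Department of UZ Brussel" in the extended protocol and "At least 70 selected patients presenting to the Emergency Department of UZ Brussel" in the short one. No group sizes, expected means or SDs appear in either.

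**The concern.** Standard ANCOVA estimates one residual variance from both groups together. With equal groups, a difference in spread hardly affects the test. With unequal groups, the larger group dominates the pooled estimate. If the smaller group is the more variable one, the standard error is too small and false positives increase. If the larger group is the more variable one, the standard error is too large, real differences are missed and intervals are too wide.

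Both conditions are realistic here. Nothing in the plan controls the split. On a scale bounded at zero, a group with little pain tends to have less spread than a group with more, so a real treatment difference may well bring a variance difference with it. The more variable group could also change between the three time points, so a reader could not correct for the error afterwards.

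The Improvement Pathway in the short protocol says that a confirmed hypothesis could lead to LAT gel replacing infiltration for specific indications, so the stated error level matters.

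**Working it through.** **The plan's own figure.** The short protocol says its minimum of 70 rests on internal data and a power calculation, but gives no inputs, so the figure cannot be reproduced. Solving backwards with an assumed two-sided 5% level, 80% power and equal groups: n per group = 2(1.96 + 0.84)²/d² = 15.7/d², and n = 35 gives d of about 0.67 SD. N=70 is used below.

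**Inputs.** From the documents: N=70, ANCOVA, three VAS outcomes, no controlled split. Assumed: two-sided 5%, one covariate, splits of 35/35, 28/42 and 18/52, SDs of 25 and 12 mm.

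**Formula.** With group sizes n1, n2 and SDs s1, s2:

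- true variance of the difference: V = s1²/n1 + s2²/n2
- variance used by the pooled analysis: P = sp²(1/n1 + 1/n2), with sp² = [(n1−1)s1² + (n2−1)s2²]/(N−2)
- q = √(V/P); approximate type I error = 2[1 − Φ(1.996/q)], where 1.996 is the t critical value on 67 df

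When q = 1 this approximation returns 4.6% rather than 5%.

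**Numbers put in.**

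| Smaller/larger group | SD smaller/larger | V | sp² | P | q | Type I error |
|---|---|---|---|---|---|---|
| 35/35 | 25/12 | 21.97 | 384.5 | 21.97 | 1.00 | 4.6% |
| 28/42 | 25/12 | 25.75 | 334.99 | 19.94 | 1.14 | 7.9% |
| 28/42 | 12/25 | 20.02 | 434.01 | 25.83 | 0.88 | 2.3% |
| 18/52 | 25/12 | 37.49 | 264.25 | 19.76 | 1.38 | 14.7% |
| 18/52 | 12/25 | 20.02 | 504.75 | 37.75 | 0.73 | 0.6% |

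Example, fourth row: V = 625/18 + 144/52 = 37.49; sp² = (17×625 + 51×144)/68 = 264.25; P = 264.25 × (1/18 + 1/52) = 19.76.

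**Simulation.** ANCOVA with one covariate at 18/52 gave 15.9% (SDs 25/12), 0.9% (12/25) and 9.1% (20/15), and about 5% at 35/35. The 28/42 split with SDs of 25 and 12 gave about 3% to 9%, depending on which group was more variable.

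**Is the floor the cause?** No. Skewed, bounded scores with equal SDs gave 4.8% at 18/52.

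**Does a larger N help?** No. At an 80:20 split with an SD ratio of 2 and the smaller group more variable, the formula gives 17.3% at N=50, 17.5% at N=70 and 17.6% at N=100.

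**Intervals.** Assume LAT mean 5, SD 8, and lidocaine mean 40, SD 25. The pooled 95% interval covers 82.8% at 49 LAT/21 lidocaine, 94.8% at 35/35 and 99.1% at 21/49.

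**Effect of HC3.** In the same interval scenario, non-coverage becomes 5.6%, 4.8% and 4.3%. For type I error with equal means and skewed scores, HC3 is less complete when the smaller group is more variable:

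- 18/52: 7.7% to 9.2%
- 49/21: 13.1% falls to 7.3% (SDs 10 and 20), and 17.6% to 8.4% (SDs 8 and 24)
- 56/14: 19.3% falls to 9.6%, and 26.9% to 11.4%, for the same SD pairs

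**The case against.** **The damaging inputs are assumed.** This is correct. The documents state no split, SD or failure rate. LAT gel is one of two listed treatment options, so near balance, or an excess of LAT, is possible. The point is therefore conditional: the plan does not prevent the harmful combination.

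**Which group will be more variable?** A reader might infer that LAT will fail more often and so spread more. The documents do not support that; the Introduction describes it as at least equivalent. The Procedure also provides supplementary infiltration when testing shows insufficient anaesthesia, so spread caused by failures should shrink before suturing pain is scored.

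**Is the floor enough by itself?** A reader might infer that zero-heavy VAS scores alone invalidate ANCOVA, or that a rank test should supply the main p-value. Neither follows. Rank ANCOVA is itself off level at 18/52: 9.9% with SDs 25/12 and 2.3% with 12/25. It also tests a different null: with equal means and skewed scores at an SD ratio of about 2, it rejected 64% to 70% of the time. Its power advantage depends on the scenario. With 60% versus 30% zeros and the same tail, power was 34% for means and 61% for ranks. With 50% zeros in both groups and different tails, it was about 35% against 11%.

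**Clustering.** A reader might infer that patients cluster within physicians who each favour one method. The documents give no number of physicians, intraclass correlation or pattern of use. The data collection form is not reproduced, so a missing physician identifier cannot be claimed.

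**Larger problems exist.** Physician-chosen allocation and an underspecified SAP threaten validity more than the variance assumption does. That stands, but it is no reason to keep a standard error that can be improved at almost no cost.

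**Conclusion.** The concern holds as a conditional one. The common-variance assumption is a property of standard ANCOVA, not wording in the SAP, and unequal groups are a reasonable inference, not a stated fact. If size and spread both differ, the nominal 5% can become anything from about 1% to about 16% at 18/52 with SDs of 25 and 12, or about 3% to 9% at 28/42. With either equal groups or equal SDs it stays near 5%. The error can go in either direction and may differ across the three time points. All these figures rest on assumed splits and SDs. This is an inexpensive improvement to the analysis, not evidence that the results will be wrong.

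**What to change.** Add to the SAP that the ANCOVA-adjusted mean difference is the primary estimate at each time point, and that its standard error, p-value and 95% interval are heteroscedasticity-consistent (HC3).

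A rank-based or proportional-odds analysis with the same covariates may be reported as a sensitivity analysis only, because it tests a different null. If the treating physician can be identified from the form or the emergency report, report a further sensitivity analysis that allows for physician.

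The cost is SAP wording and a little extra analysis; no patients or procedures are added. Intervals may be slightly wider when variances are in fact equal. HC3 is not a full repair when the smaller group is small, skewed and more variable (about 7% to 9% at 18/52, more in smaller groups). Even with equal SDs, skewed scores and only 14 in the smaller group gave 6.4%, against 5.0% for the pooled analysis. HC3 does nothing about confounding by physician-chosen treatment, which needs its own handling.
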